## 0. Study synopsis

Study title	Gynecologists' feedback on ART-Pregnancy rates: a Randomized Controlled Trial
Short title	GAP-RCT
Sponsor name	KU Leuven
Principal Investigator	[name]. [name] (UZ Leuven)
Medical condition/ disease under investigation	Infertility treated with IVF
Study purpose	
We will examine the hypothesis that women who are given their personalized IVF-prognosis are less likely to overestimate their IVF-live birth rate, as compared to women who do not receive a personalized IVF-prognosis.
 
Control group: At the time of their fresh embryo transfer couples will receive a document with a photo of their transferred embryo(s) and the number of cryopreserved embryos.
 
Intervention group: At the time of their fresh embryo transfer couples will receive a document with the following feedback: a photo of their transferred embryo, the number of cryopreserved embryos, the quality rating of the transferred embryo's (i.e. ★, ★★, ★★★, ★★★★), and couple's personalized IVF-prognosis (i.e. their chance on a live birth from the current IVF-cycle, including the transfer of fresh and if available cryopreserved embryos, calculated by entering eight background characteristics and five IVF-laboratory results into a prognostic model).

Primary outcome	The proportion of women expecting their IVF-live birth rate to be double their calculated IVF-prognosis , directly after their fresh embryo transfer.
Secondary outcomes	
The proportion of men expecting their IVF-live birth rate to be double their calculated IVF-prognosis, directly after their fresh embryo transfer.
 
Women's and men's anxiety will be assessed with the reliable 'State-Anxiety Inventory, (STAI-state)' questionnaire, disseminated in coded paper-pencil format on the day of the fresh embryo transfer.
 
Patient's infertility-specific distress will be assessed with the reliable 'Infertility Distress Scale (IDS)' questionnaire, disseminated via text message and online within two days of the conclusive pregnancy test after the transfer of the last (fresh or cryopreserved) embryo of the studied IVF-cycle.

Background variables	The following variables that potentially affect patient's expected live birth rate will be extracted from patient's medical file: whether they already had an ART-child (i.e. yes/no) and how many unsuccessful embryo transfers they had in the past (i.e. number). In addition, both partner's general optimism, will be assessed with the reliable questionnaire 'LOT-R' which will be disseminated in coded paper-pencil format on the day of oocyte aspiration.
Feasibility outcome	On the day of their fresh embryo transfer, men and women will be asked to fill out two questions on uptake and evaluation of the standardized personalized feedback.

Follow-up outcomes	Long-term clinical and compliance outcomes will be followed-up in couple's medical chart 12-18 months after the oocyte aspiration. More specifically, the 12-months cumulative clinical live birth rates for the observed oocyte aspiration will be extracted from the medical chart. In addition, the following compliance outcomes will be extracted: (i) censored by their medical doctor to discontinue IVF (yes-no) , (ii) number of untreated cycles within 12-months after oocyte aspiration and prior to the start of a new fresh cycle while not pregnant (i.e. IVF-delay), (iii) whether or not a subsequent IVF-cycle was started within twelve months after the last failed pregnancy test while not pregnant and no medical censoring to discontinue (i.e. IVF-discontinuation).
Study design	RCT (computerized randomization; 1/1 allocation sequence; no blinding)
Endpoints	The expected IVF live birth rate, anxiety and infertility specific distress of women and men.
Sample size	Hypothesizing that the intervention can lower the proportion of women expecting their live birth rate to be double their calculated IVF-prognosis from 50% to 25% dictates a sample size of 64 women per group (two-sided test; power 80%; $\alpha=0.05$ ; G*Power). To account for a 15% chance of study drop-out due to not filling-out the questionnaires or loss of follow-up, 74-80 women will be recruited per group .
Summary of eligibility criteria	
Inclusion criteria: Couples treated with a 2nd-6th fresh cycle of IVF (i.e. IVF with or without ICSI; every couple can only participate ones in this study).
 
Exclusion criteria, Couples treated with:
 
 
• Pre-implantation Genetic Diagnosis (PGD)
 
• donated oocytes, sperm or embryos
 
• Spermatozoa obtained by testicular extraction (ICSI-CRYO-TESE)
 
• HIV-positive diagnosis
 
• Embryo transfer on day 2
 

Maximum duration of study participation for a subject	Study participation will be during one IVF-cycle. Men and women of eligible couples will be asked to each fill out a questionnaire on the day of oocyte aspiration, on the day of fresh embryo transfer and within two days of the pregnancy test after the transfer of the last embryo. Filling out each questionnaire takes 5 minutes.
Version and date of final protocol	Version 3, September 30, 2019
Version and date of protocol amendments	Not applicable

## 1. Background and rationale

The general population is known to overestimate *in vitro* fertilisation (IVF) success rates. Qualitative interviews showed that well informed women cryopreserving their oocytes were unrealistically optimistic about their own chances of having a child as they thought they and/or their gynaecologist were better than average. To the best of our knowledge, the live birth rates expected by infertile couples during their IVF-cycle (i.e. in real life treatment situations) has yet to be studied. In addition, whether these expected live birth rates are affected by factors like gender, previous treatment experiences and level of optimism is unknown.

IVF-success rates expected by patients are especially relevant since patients shared in interviews that the combination of unrealistically high expected live birth rates and repeated unsuccessful IVF-cycles, caused distress, which ultimately led to discontinuation from IVF. The association between patient's expected IVF-success rates and their level of distress experienced at the time of a negative pregnancy test and decision to discontinue IVF has yet to be quantified prospectively.

Fertility patients have indicated that they want personalized information, for example on which success rate to expect. Recently, prognostic models that calculate personalized and cycle-specific success rates, have been developed and validated. So far, no study has examined whether gynaecologist's feedback to couples about their personalized IVF-prognosis influences patient's expected IVF-success rate.

Based on retrospective analysis of data from couples treated with a 2nd - 6th IVF-cycle by our laboratory, our group developed a model to give couples a personalized IVF-prognosis on the day of their embryo transfer based on eight background characteristics and five IVF-laboratory results from their current IVF-cycle. Our prognostic model performs exceptionally well as compared to previously published models. More specifically, our model has a c-statistic of 0.74 and the c-statistic of previously published IVF-models ranges between 0.50 and 0.73

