## 2. Study objectives and design

### 2.1 Study objective

We will examine the hypothesis that women who are given their personalized IVF-prognosis are less likely to overestimate their IVF-live birth rate, as compared to women who do not receive a personalized IVF-prognosis.

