## 3. Methodology

### 3.1 Study population and sample size

#### 3.1.1 Study population

##### Inclusion criteria:

All couples treated at the Sint Augustinus Fertility clinic (Wilrijk) with a 2nd-6th fresh cycle of IVF are eligible. IVF includes IVF with or without ICSI and every couple can only participate ones in this study. Couples treated with their first IVF-cycle are not eligible, since they are not the priority target population for this study. According to qualitative research discontinuation from IVF can amongst others be explained by the combination of high expectations regarding IVF-live birth rates and having experienced several cycles of unsuccessful IVF.

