### 4.2 IVF-live birth rates expected by patients

The IVF-live birth rates expected by patients will be analysed for both groups and for men and women separately. We will conduct an intention to treat analysis, primarily focussing on whether the intervention and the control group differ in the likeliness that women expect a live birth rate, which is at least twice as big as their prognosis. The difference in this binominal outcome will be analysed with a Chi-test. A p-value  $\leq 0.05$  will be considered statistically significant. To also inform readers about the extent of the potential difference, proportions of the primary outcome will be reported per group and the 95% confidence interval of the difference in proportions of the primary outcome between both groups (i.e. if significant, it will not include 0) will also be reported.

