### 4.3 Quantification of the under/over estimation of the live birth rates expected by patients

In addition to the primary outcome (i.e. evaluating the proportion of women expecting their IVF-live birth rate to be double their calculated IVF-prognosis directly after their fresh embryo transfer) we want to quantify this under/over estimation. This will be calculated using the following formula: (expected LBR-prognosis)/prognosis. A positive sign shows overestimation, a negative sign shows underestimation and the absolute value quantifies the extend of the over/underestimation. For both groups, the mean and SD will be calculated. In addition, the mean difference in misjudgement between both groups and its 95% confidence interval (i.e. to give an impression of the preciseness of this estimation) will be reported.

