#### 4.7 Follow-up outcomes

Whether the intervention and control group, differ in one long-term clinical (i.e. the 12-months cumulative clinical live birth rates for the observed oocyte aspiration) and three compliance outcomes, followed-up in patient's medical chart, will be analysed. The association between expected live birth rates and these long-term outcomes will also be explored on data from the entire sample.

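### Overestimation is scored against the absolute prognosis, but the plan reports only the model's discrimination and never compares the prognosis with observed live births

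*Combined protocol and SAP*

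**What the plan says.** The objective in Section 2.1 is that "women who are given their personalized IVF-prognosis are less likely to overestimate their IVF-live birth rate" than women who are not given it. Section 2.2 gives the first aim as more realistic expectations. Both are statements about the truth.

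The yardstick is the calculated prognosis:

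- **Primary endpoint (Sections 2.3 and 4.2):** whether "women expect a live birth rate, which is at least twice as big as their prognosis".
- **Misjudgement measure (Section 4.3):** expected rate minus prognosis, divided by prognosis. "A positive sign shows overestimation, a negative sign shows underestimation".

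On the model's performance, Section 1 says "our model has a c-statistic of 0.74", and adds that "the c-statistic of previously published IVF-models ranges between 0.50 and 0.73". Its remark about validation concerns published models. The trial uses an adapted model that the group developed on retrospective data from its own laboratory. Appendix 7 lists coefficients, standard errors and p-values, but no calibration intercept, slope or observed/expected ratio.

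Section 4.7 compares the arms on "the 12-months cumulative clinical live birth rates for the observed oocyte aspiration" and three compliance outcomes. It also explores how patients' expected rates relate to those outcomes. The prognosis itself is not set against the births anywhere in Section 4.

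**The concern.** A c-statistic does not change under any monotone increasing transformation of the predictions. A model could rank couples with a c-statistic of 0.74 and still be too low or too high for everyone. Both measures depend on the absolute value, so the evidence offered does not cover the use made of the model.

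This matters because women in the intervention arm are shown the number against which they are then scored. A positive result is expected if they simply adopt it. Whether adopting it also brings them nearer to their real chance depends on calibration, which is neither reported nor planned to be checked. At stake is the reading of the result as less overestimation or more realism, not the existence of a difference between arms.

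**Working it through.** **The plan's own figures.** The c-statistic cannot be recomputed from the documents. The sample size can: for 50% against 25%, two-sided 0.05, the exact power of Fisher's test is 79.4% with 63 per group and 80.2% with 64. The 64 per group in Section 3.1.2 reproduces, and nothing below alters it.

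**Can calibration be judged from Appendix 7?** No. No calibration statistic is given, and the age-squared and age-cubed coefficients are printed as 0.000. At an assumed age of 36, half a rounding unit is worth 0.0005 × 36² = 0.65 and 0.0005 × 36³ = 23.3 on the logit scale, so the absolute prognosis cannot be rebuilt from the printed table. This concerns the printed precision, not necessarily the precision used at the clinic.

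**Effect on the doubling cut-off.** Let k = true chance / prognosis. Then 2 × prognosis = (2/k) × true chance.

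- k = 0.7: 2/0.7 = 2.86 times the true chance
- k = 1.0: 2.00 times
- k = 1.3: 2/1.3 = 1.54 times

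A flagged woman could be right only if k were 2 or more.

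**Effect on the proportions (illustration).** Assume that expected/prognosis is lognormal with log-SD 0.6 and medians set to give the planned 50% and 25%. The proportions truly at or above double the real chance would be:

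| k | Control | Intervention |
|---|---|---|
| 0.8 | 64.5% | 38.1% |
| 1.0 | 50% | 25% |
| 1.25 | 35.5% | 14.8% |

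The direction holds throughout; the reported extent of overestimation moves.

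**Effect on the signed measure.** This has no factor-of-two margin.

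- A woman who expects exactly her true chance scores k − 1: +0.30 at k = 1.3 and −0.30 at k = 0.7. She is labelled as over- or underestimating although she is right.
- A woman who adopts the prognosis scores 0. Her error relative to the truth is 1/k − 1: −0.23 at k = 1.3 and +0.43 at k = 0.7.

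**What the trial could estimate.** The half-width of the 95% CI for observed minus mean predicted is about 1.96 × √(p(1 − p)/n). The documents give no mean live birth rate. I assume p from 0.30 to 0.384, the upper value being the specimen prognosis of 38.39% in Appendix 5. For n, 128 is 2 × 64 and 160 is 2 × 80.

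| n | p = 0.30 | p = 0.384 |
|---|---|---|
| 128 | ±7.9 points | ±8.4 points |
| 160 | ±7.1 points | ±7.5 points |

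The relative miscalibration detectable with about 80% power is 2.8 × √(p(1 − p)/n)/p. This is 38% at n = 128, p = 0.30, and 28% at n = 160, p = 0.384. The 160 is a ceiling, because the recruitment target in Section 3.1.2 allows for couples who have no embryo to transfer.

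**Does the planned outcome match the prognosis?** Not as defined. Section 2.2 defines the prognosis over the fresh and all frozen transfers of the cycle, without a stated time limit. The synopsis and Section 2.4 define live birth cumulatively over 12 months for the aspiration, read from the chart at 12 to 18 months after aspiration. Section 3.2 instead puts the chart review eighteen months after the last transfer, and its list of items omits live birth. A strict 12-month birth window would miss births from later frozen transfers and bias observed/expected downward.

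**The case against.** The strongest reply is that the endpoint is openly defined against the calculated prognosis and that both arms use the same formula. Randomisation therefore protects the comparison, and type I error, power and sample size do not depend on calibration. All of that stands. A reader might infer that the primary test is biased; it is not.

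A reader might also infer that women flagged as overestimating could in fact be right. The doubling margin prevents this unless the true chance is at least twice the prognosis, and nothing in the documents suggests an error of that size. The point bears mainly on the signed measure, on women who are not flagged, and on the wording of the conclusion.

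Nor do the documents show that the model is miscalibrated, that it was never checked, or that it comes from a laboratory unlike the trial clinic's. Section 1 simply does not report calibration, and a protocol background need not reproduce a full validation. The range 0.7 to 1.3 is hypothetical.

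Finally, the sample is small and the defined live birth outcome does not fit the prognosis. Both objections are correct. They limit what can be added: an overall observed-against-predicted comparison is worthwhile, while a calibration slope or a re-scored primary endpoint would be too imprecise to be more than optional.

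**Conclusion.** The point holds as a cheap improvement. The plan reads distance from the calculated prognosis as distance from the truth, supports this only with a measure of ranking, and leaves unused an opportunity to check it. The between-arm test stands as planned. Proportional miscalibration of 0.7 to 1.3 would move the cut-off to 2.86 to 1.54 times the true chance. It would shift the signed score of a correctly informed woman by −0.30 to +0.30. What is unsupported is the claim that expectations became more realistic, as distinct from closer to the number given.

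These sizes assume one common ratio k for all couples. The precision of about ±7 to 8 points assumes 128 to 160 couples with a transfer and a live birth rate of 30 to 38%. Only gross miscalibration could be detected.

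**What to change.** 1. **Reconcile the follow-up first.** Align the synopsis, Section 2.4 and Section 3.2 on when the chart is reviewed and whether live birth is extracted then. State whether the 12-month limit applies to the birth or to the conception. Appendix 5 labels the number in Dutch as a pregnancy chance, so confirm that live birth is the target.
2. **Add to Section 4.7** a prespecified exploratory calibration-in-the-large: observed against mean predicted live birth, with a 95% CI, in all randomised couples with a transfer. Count live births from all fresh and frozen transfers of the studied aspiration, as recorded at the planned chart review.
3. **Word the conclusion accordingly.** Unless calibration is shown to be acceptable, report results as relative to the calculated prognosis.
4. **Optional, labelled exploratory:** a calibration slope, a sensitivity analysis of the primary endpoint with recalibrated prognoses, and any calibration already available from the development data.

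The cost is a small change to the live birth definition taken from the chart, possibly somewhat longer extraction, and one extra analysis whose imprecision must be stated. Randomisation, sample size and the primary test do not change.

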## 2. Study objectives and design

### 2.1 Study objective

We will examine the hypothesis that women who are given their personalized IVF-prognosis are less likely to overestimate their IVF-live birth rate, as compared to women who do not receive a personalized IVF-prognosis.

### 2.2 Study design

At the time of oocyte aspiration, patients will be randomised in two groups:

- Control group: At the time of their fresh embryo transfer couples will receive a document with a photo of their transferred embryo(s) and the number of cryopreserved embryos.
- Intervention group: At the time of their fresh embryo transfer couples will receive a document with the following feedback (Appendix 5): a photo of their transferred embryo, the number of cryopreserved embryos, the quality rating of the transferred embryo's (i.e. ★, ★★, ★★★, ★★★★, appendix 6), and couple's personalized IVF-prognosis (i.e. their chance on a live birth from the current IVF-cycle, including the transfer of fresh and if available cryopreserved embryos), calculated by entering eight background characteristics and five IVF-laboratory results into a prognostic model (Appendix 7).

Firstly, we wish to analyse whether personalized information on IVF-prognosis on the day of their fresh embryo transfer results in more realistic expected IVF-live birth rates.

Secondly, we wish to evaluate whether sharing these IVF-prognosis with patients at the time of embryo transfer is associated with the anxiety experienced by patients.

Thirdly, we wish to explore whether these IVF-live birth rates expected by patients are associated with the infertility specific distress experienced by patients at the time of a negative pregnancy test.

Fourthly, we wish to follow-up whether these IVF-live birth rates expected by patients are associated with clinical and compliance outcomes.

### 2.3 Study parameters/endpoints

The **primary endpoint** is the proportion of women expecting directly after their fresh embryo transfer that their IVF-live delivery birth rate to be double their calculated IVF-prognosis (i.e. women's expected live birth rate  $\geq 2^* \text{prognose}$ ) In addition the proportion of men expecting their IVF-live birth rate to be double their calculated IVF-prognosis will be studied. Patient's expected IVF-live birth rates will be assessed immediately after the fresh embryo transfer with a single question coded paper-pencil questionnaire.

**Women's and men's anxiety** will be assessed with the reliable 'State-Anxiety Inventory, (STAI-state)' questionnaire disseminated in coded paper-pencil format on the day of the fresh embryo transfer (Appendix 3). The STAI-state questionnaire includes 20 questions rated on a-four-point-Likert scale and results in a score between 20 to 80 (the higher, the more anxiety).

**Patient's infertility-specific distress** will be assessed with the reliable 'Infertility Distress Scale (IDS)' questionnaire, which has been translated reciprocally to Dutch (Appendix 4). The IDS questionnaire will be disseminated via text message and online within two days of the conclusive pregnancy test after the transfers of the last (fresh or cryopreserved) embryo of the studied IVF-cycle. The IDS questionnaire includes eight questions to be rated on a-five-point-Likert scale and results in a score between 8 and 40 (the higher, the more infertility specific distress, Appendix 4).

### 2.4 Follow-up parameters/endpoints

**Long-term clinical and compliance outcomes** will be followed-up in couple's medical chart twelve-eighteen months after the oocyte aspiration. More specifically, the 12-months cumulative clinical live birth rates for the observed oocyte aspiration will be extracted from the medical chart. In addition, the following compliance outcomes will be extracted: (i) censored by their medical doctor to discontinue IVF, (ii) number of untreated cycles within 12-months after oocyte aspiration and prior to the start of a new fresh cycle while not pregnant (i.e. IVF-delay), (iii) whether or not a subsequent IVF-cycle was started within twelve months after the last failed pregnancy test while not pregnant and no medical censoring to discontinue (i.e. IVF-discontinuation;)

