### 3.2 Study procedures including recruitment and data-collection

The main outcomes of this study are gathered on the days of OPU and Embryo transfer as presented in figure 1.

[figure not shown]

Figure 1: Study procedure and data collection for participating couples of the GAP-RCT

**On the day of their oocyte aspiration**, couples will be informed on the study and asked for their informed consent. Consenting men and women of eligible couples will be asked to each fill out a questionnaire on expected live birth rate (Appendix 1) and the LOT-R questionnaire (Appendix 2) on general optimism.

**On the day of their fresh embryo transfer**, couples are randomized. Couples in the control group receive a document with a photo of their embryo(s) and the number of cryopreserved embryos. Couples in the intervention group receive a document with a photo of their transferred embryo(s), its quality rating, the number of cryopreserved embryos and couple's personalized IVF-prognosis (Appendix 5). Men and women of both groups will be asked to fill out the questionnaire on expected live birthrate (Appendix 1) and the STAI-state questionnaire on anxiety (Appendix 3).

**Within two days of the conclusive pregnancy test** after the transfers of the last (fresh or cryopreserved) embryo of the studied IVF-cycle, the IDS questionnaire on Patient's infertility-specific distress will be disseminated via text message and online (appendix 4).

**Eighteen months after the embryo transfer** of the last (fresh or cryopreserved) embryo of the studied IVF-cycle, the researchers will follow-up the long-term clinical and compliance outcomes in patient's medical chart (i.e. censored by their medical doctor to discontinue IVF, IVF-delay and IVF-discontinuation).

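### IVF-discontinuation and IVF-delay cover treatment at any clinic, but their only stated source is the medical chart in a one-clinic trial, so cycles started elsewhere will often be missed

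*Combined protocol and SAP*

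**What the plan says.** Section 2.4 and the synopsis (section 0) define IVF-discontinuation by "whether or not a subsequent IVF-cycle was started within twelve months after the last failed pregnancy test while not pregnant". Couples whose doctor ended treatment are set aside by a further condition, "and no medical censoring to discontinue". Neither place says at which clinic the cycle must be started. IVF-delay is the number of untreated cycles in the 12 months after aspiration, before a new fresh cycle and while not pregnant, again with no clinic named.

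The source is the same wherever one is named:

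- Section 2.4: the outcomes "will be followed-up in couple's medical chart twelve-eighteen months after the oocyte aspiration".
- Section 3.2: "the researchers will follow-up the long-term clinical and compliance outcomes in patient's medical chart".
- Section 4.7: "three compliance outcomes, followed-up in patient's medical chart, will be analysed", both as a comparison of arms and, in the whole sample, in relation to expected live birth rate.
- The synopsis also names the couple's chart.

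Section 3.1.1 restricts recruitment to one named fertility clinic. The last questionnaire is the distress scale, sent "Within two days of the conclusive pregnancy test" that follows the last transfer of the studied cycle (section 3.2). Section 2.5 states that there is no blinding.

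**The concern.** The defined event is a cycle started anywhere. The stated source can reliably show only what reaches the chart of a couple recruited at one clinic. If a couple moves and nobody records it, the chart falls silent in the same way as for a couple that stopped treatment, and the two cannot be told apart. For IVF-delay, cycles treated elsewhere look untreated.

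This matters because discontinuation is part of the trial's rationale. Section 1 describes a path from unrealistic expectations and failed cycles, through distress, to giving up IVF. Section 3.1.1 uses the same argument to leave out first cycles, and section 2.2 makes the link between expectations and compliance outcomes the fourth aim. Changing clinic is a different behaviour from giving up. If the two are mixed, the absolute rate is overstated and the association with expected live birth rate may partly describe couples who went elsewhere.

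**Working it through.** **Step 1. Is there any route by which treatment elsewhere would be seen?** The documents were checked for each possible route.

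- Patient report: none. The last study contact comes at the pregnancy test, which is when the 12-month discontinuation window opens.
- Registry linkage or requests to other clinics: none is described.
- Coding rule for couples who transfer or disappear from the chart: none. Pregnancy and medical censoring are the only stated exclusions.
- Loss to follow-up: mentioned only as an allowance in the sample size (synopsis and section 3.1.2).
- Withdrawal (section 3.3): covers couples who stop taking part in the study. A couple that changes clinic has not withdrawn.

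A transfer noted in the chart could be caught by chance, but nothing says how it would be coded.

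**Step 2. Figures in the plan.** There is no expected rate, sample size or power for discontinuation. The 64 per group in section 3.1.2 concerns the primary outcome and has no bearing here. Every rate below is therefore an assumption.

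**Step 3. Size of the error within an arm.** Let d be the true discontinuation rate and m the share of truly continuing couples whose cycle elsewhere is not seen. If unseen couples are counted as discontinued:

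recorded rate = d + (1 − d) × m

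| d | m = 5% | m = 10% |
|---|---|---|
| 20% | 0.20 + 0.80 × 0.05 = 24% | 0.20 + 0.80 × 0.10 = 28% |
| 30% | 0.30 + 0.70 × 0.05 = 33.5% | 0.30 + 0.70 × 0.10 = 37% |

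**Step 4. Effect on the comparison of arms when m is equal.** The recorded difference is (1 − m) × (true difference).

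- No true difference: none is created.
- True 20% versus 30%, m = 10%: recorded 28% versus 37%, so 10 points shrink to 9.
- True 15% versus 30%, m = 10%: recorded 23.5% versus 37%, so 15 points shrink to 13.5. With an assumed 50 evaluable couples per arm, power falls from 43% to 31%.

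**Step 5. Effect when m differs by arm.** With the same true d in both arms, the false difference is (1 − d) × (m1 − m0). The rejection rates are for a two-sided pooled z-test at 0.05, with an assumed 40-60 evaluable couples per arm.

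| m0 versus m1 | d = 20% | d = 30% | Rejection rate (nominal 5%) |
|---|---|---|---|
| 5% versus 15% | 24% versus 32%: 8 points | 33.5% versus 40.5%: 7 points | 10-16% |
| 5% versus 20% | 24% versus 36%: 12 points | 33.5% versus 44%: 10.5 points | 16-30% |

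For scale, at 50 per arm the standard error of the 24% versus 32% difference is √[(0.24 × 0.76 + 0.32 × 0.68)/50] = √(0.400/50) = 0.089, about 9 points.

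**The case against.** Four objections deserve an answer.

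- **The source.** A reader might infer that the plan reads only the trial clinic's own in-house records. The text says the couple's or patient's chart, and the synopsis takes earlier unsuccessful transfers from the medical file without limiting them to one clinic. So the clinic-only reading is an inference. It remains the natural one: there is one recruiting clinic and no other source, and a file that holds past history need not receive later treatment elsewhere.
- **The coding.** A reader might infer that the plan scores transferred couples as discontinued. No passage says so, and under the definition a known cycle at any clinic counts as continuation. The overcount comes from couples whose move is not seen. This objection stands as to wording but does not remove the problem.
- **Bias between arms.** A reader might infer that a low printed prognosis drives couples to other clinics and so biases the comparison. The documents give no evidence of this, nor of its direction. With equal transfer there is no false difference, and the 8-point example needs an assumed threefold imbalance and is still below one standard error at 50 per arm. This objection stands.
- **Importance.** These are follow-up outcomes, unpowered, and section 4.7 names no test for them. That limits the weight of the point. It does not excuse a source that cannot reliably show the event it is meant to record.

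**Conclusion.** The concern holds as a mismatch between definition and source. The outcomes cover IVF at any clinic, while the plan relies on charts that, on the natural reading, will often miss treatment elsewhere. The expected result is a discontinuation rate that is too high: 24-28% recorded for a true 20%, if 5-10% of continuing couples move unseen and are counted as having stopped. IVF-delay is overstated in the same direction.

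Bias between arms is a possibility only. It requires transfer to differ by arm, which an unblinded design permits and the documents do not show. If transfer is equal, the cost is modest dilution of any true difference. The primary outcome, the men's expectations, anxiety and distress do not depend on this source and are unaffected. The point should be settled before any result on IVF-discontinuation is reported.

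**What to change.** **Preferred.** Twelve months after the last failed test, send one closed question through the text-message and online route already used for the distress scale: new cycle started here, started elsewhere, or none. Code elsewhere as continued. For non-responders use the chart, and code those with no chart evidence of a new cycle as unknown. Report the number unknown by arm, and run a sensitivity analysis counting all unknowns first as discontinued and then as continued. Within an arm those two rates differ by exactly the share unknown, so the reader sees how much rests on missing answers. If IVF-delay is to be corrected too, the message must also ask when the cycle started; otherwise label that outcome as limited to this clinic. The chart must be read after the 12-month window closes; sections 2.4 and 3.2 give different review times, a separate matter to reconcile.

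**If no contact is wanted.** Rename the outcome as no further cycle at this clinic, count transferred couples as events under that label, report documented transfers by arm, and draw no conclusion about discontinuation of IVF as such.

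**Cost.** The first option needs one extra message with consent wording and will meet some non-response, which may itself differ by arm. The second changes only the label, the coding and the scope of the conclusion, and gives up the question about stopping IVF. Neither changes the sample size.
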